Effects of ECAS and underlying processes: For those that have joined ECAS, we will test how engagement with the ECAS Facebook page and group relates to (i) a sense of social connection and (ii) how both engagement and the sense of social connection relate to the interim outcomes of increased health literacy, covid protective behaviour and community champion activity (see Figure 2). A further analysis will compare levels of each of these factors amongst those who did engage with the intervention versus a comparator group who did not and across socio-demographic groups if the data allows (i.e., using moderation analyses). Amongst both samples, we will also measure current levels of mental health and test relationships between these and each factor. These analyses will provide a quantitative evaluation of the extent to which the intervention met its aim to ‘inform’, ‘prevent’ and ‘assist’. Additionally, for those who engage in it, it will also identify which interim outcomes were most impacted and the extent to which this effect was mediated by social connection.

[figure not shown]

Figure 2: Primary conceptual model to be tested.

Given the nature of the study, much of these data will be retrospective (i.e., people’s recollection of their behaviours). In these instances, we will ask participants to recall how they felt during what our preparatory work with stakeholders (stakeholder workshops and also a PPIE workshop), identified as a *critical phase* of the intervention’s deployment. The critical phase selected for the quantitative analysis of new data is the the first two weeks following the lifting of the first lockdown.

Table 1 (see below) indicates broad operationalisations of each of the factors, the source of data (and whether it is current or retrospective) and possible measurement instruments.

Table 1: Indicative primary outcome measures¹

Factor	Operationalisation(s)	Source of data	Indicative instrument
Interaction with ECAS	Did / did not engage with site Intensity of engagement (users only)	Facebook data or self-report	Study generated scale/metrics
Social connection	Sense of social connection with others Collective responsibility	Self-report (current) Self-report (critical phase)	Validated scale (Lee, Draper & Lee, 2001)
Health literacy	Level of perceived digital health literacy	Self-report (current)	Use of two subscales: information searching and evaluating reliability from validated scale (Van der Vaart & Drossaert, 2017)

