Sentiment analysis: Sentiment analysis, through use of Linguistic Inquiry and Word Count (LIWC) software, will computationally assess affective change for individuals using the ECAS Facebook group. The corpus will be consistent with that selected for psychological discourse analysis within Work Package 2 (see below), for consistency, to enable triangulation and heighten human monitoring of content. Our evaluation will test the extent to which negative affect in member discussion around protective health action topics decreased over time between the critical periods, and also the extent to which positive affect in response to ECAS dissemination of public health messages increases.

Health equity: To evaluate how widely and amongst how diverse a population the intervention was accessed we will compare the demographic of people using ECAS against the demographic profile of Essex. This analysis will include data from the core provision (Facebook) but also other platforms where ECAS presented information (i.e., Instagram, Twitter).

Work Package 2: Qualitative work package

The qualitative strand of the project will examine which factors were important in contributing to the outcomes of:

- Achieving improved health literacy;
- Encouraging protective health actions;
- Enhancing community connectedness and mutual aid.

It will also explore how the digital community development approach sought to achieve whole system change for the public health function.

The overall approach is *digital ethnography*, also known as online or cyber ethnography, which seeks to study online communities and their cultures (Caliandro, 2014). It adapts the traditional methods of participant observation, interviews, documentary analysis and surveys

to studying online communities. Digital ethnography will be used to analyse online interactions between people connected through technology.

The qualitative work stream will have two components:

Qualitative component 1: Participant observation of Facebook interactions analysed using discourse analysis:

Facebook interactions in the form of posts and comments will be analysed using psychological discourse analysis (Goodman, 2017) to analyse how communication is used to mobilise social action, e.g., framing authority differently to engage members to collective action. The analysis will focus on what has been achieved through conversations rather than what the members are thinking.

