This economic evaluation has been added retrospectively to the design as the original proposal did not seek to measure cost-effectiveness or provide any form of economic analysis. The cost perspective taken in the study will be in the first instance that of the Local Authority budget holder (i.e., Essex County Council) as well as the Essex Public Health Team. The evaluation will also seek to capture and report other societal cost and benefits, that may impact on wider NHS services or on individuals and their personal time.

The economic evaluation aim is to compliment the main study with some wider understandings of the economic impact of the Essex Coronavirus Action Support (ECAS) upon Attitudes, Behaviour and public health Systems during the COVID-19 pandemic. The economic impact may be on the local authority, the public health body or individuals and will provide greater information on the resources and costs involved, potential cost savings, costs per unit of improvement in the main outcomes and any potential cost effectiveness.

All resource use, total cost calculations and costs combined with benefits to calculate potential cost effectiveness will be compared against the comparator group identified in the main methods section of the study earlier.

Specific objectives will include;

- 1) Report resource use at a total budget level in detail for the project with all its component parts such as training, salaries, office overheads, equipment alongside any other identified resources. Resources identified will be converted into summarised costs variables and their deployment and patterns of use will be described. Ultimately a total cost overall of the project will be provided.
- 2) In addition to reporting all the total costs described above, an average cost per participant will be calculated and reported. In addition the evaluation will report costs per unit of change in any of the main outcome measures on average.

The economic evaluation will compliment the existing design by using the existing outcome measures already described above (see Table 1).

3) Report all costs incurred descriptively along with patterns of resource use for the project.

For example over and above the headline reporting of total spend and averages, the evaluation will report proportions of spend. For example if training was 5% of the total spend whereas staffing costs were 70% and so on.

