Work Package 1: We will aim to recruit a sample of $n = 225$ people who have signed up to the ECAS Facebook page and group. We will also recruit a comparative, equally sized sample of Facebook users who did not sign up to the page nor recall being exposed to it. These will be either a comparative demographic profile, or we will weight responses to match our samples. Recruitment will be conducted via Facebook. The total target sample size will be $n = 450$. See *Recruitment*, below, for details on how these samples will be secured.

Inclusion criteria:

- 18+ years of age
- Facebook user
- Enrolled in ECAS page and group on Facebook (ECAS condition only)
- Works or lived in Essex during first lockdown period

Exclusion criteria:

- Enrolled in ECAS page and group on Facebook (comparator condition only)
- Unable to give informed consent

Social network analysis: Data will be collected from the ECAS group page drawing on posts made (i) during the first two weeks of the first lockdown and (ii) the first two weeks following the lifting of the first lockdown. In each period, the highest day traffic will be selected, then the lowest (non-contiguous) day and then the non-contiguous day closest to the mean. We will manually sample and code 800 contiguous interactions per day, three days per phase (total $n = 2400$ interactions).

Size of sample

Primary analysis sample: Our within condition sample of $n = 225$ allows detection of single mediation effects at power = 0.81 assuming medium (Pearson $r = .30$) relationships between variables (calculated using 'pwr2ppl' R package 'med' function). In the absence of suitable pilot data, these levels of relationship have been selected as they represent effects which are likely, and are in line with relationships between social identity and efficacy and behaviour observed in other studies (i.e., Frings, Wood & Albery, in press). Relationships smaller than that powered for are also likely to be of less practical significance. A sample sufficient to power multiple mediation models is beyond the scope of the current study.

Social network analysis: This sample size indicated above balances a manageable amount of data inputting and sufficient data to generate meaningful insight. Focusing on high and low traffic days gives a representation of time the group is seeking and receiving information from the centre of the network and times when they are engaged in more general interaction.

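### The comparator is defined by Facebook contact only, so people reached by ECAS solely on Instagram or Twitter can enter it as unexposed

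*Protocol*

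**What the plan says.** **Comparator, in prose** (Protocol, Samples and recruitment, Sampling, Work Package 1): a sample equal in size to the 225 ECAS members, made up of "Facebook users who did not sign up to the page nor recall being exposed to it". Read grammatically, the last word refers to the Facebook page.

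**Comparator, in the criteria list** (same section): the exclusion specific to this group is "Enrolled in ECAS page and group on Facebook (comparator condition only". It adds the private group to the page but omits the recall condition.

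**Other channels** (Analysis of existing data, Health equity): the assessment of how widely the intervention was accessed uses Facebook data, "but also other platforms where ECAS presented information (i.e., Instagram, Twitter".

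**The contrast** (Primary analyses of new data): levels of each factor are compared "amongst those who did engage with the intervention versus a comparator group who did not". Table 1 operationalises interaction as "Did / did not engage with site", taken from Facebook data or self-report.

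**Second use of the comparator** (Work Package 3): resource use, costs and potential cost effectiveness "will be compared against the comparator group identified in the main methods section of the study earlier".

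**Stated power** (Size of sample): the within-condition sample of 225 "allows detection of single mediation effects at power = 0.81 assuming medium" correlations of .30.

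**The concern.** The comparator is meant to represent people whom the intervention did not reach. The protocol names four places where ECAS content appeared (Facebook page, Facebook group, Instagram, Twitter), but the rules for entering the comparator refer to Facebook alone. Someone who followed ECAS on Instagram, never joined on Facebook and does not recall the Facebook page is eligible as unexposed.

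The criteria list is weaker than the prose. The section on sampling technique says that recruitment follows the inclusion and exclusion criteria. If the list alone is applied, recall of exposure is not screened at all, even for Facebook.

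If ECAS works, exposed people in the comparator shrink the observed difference. The same shrunken difference would be the denominator of any cost per unit of improvement in Work Package 3 and would make ECAS look dearer than it is. Exposure that the survey never asks about cannot be recovered at analysis, so this is not something that a later analysis plan could repair.

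**Working it through.** **1. The stated power, and whether this point touches it.** Inputs from Size of sample: n = 225, all correlations .30. Two-sided alpha of 0.05 is assumed, since none is stated. Sobel approximation:

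- a = 0.30; b = (0.30 − 0.09)/(1 − 0.09) = 0.231
- SE(a) = √(0.91/223) = 0.0639
- R² = (0.18 − 0.054)/0.91 = 0.138; SE(b) = √(0.862/(0.91 × 222)) = 0.0653
- z = ab/√(a²·SE(b)² + b²·SE(a)²) = 0.0692/0.0245 = 2.82
- power = Φ(2.82 − 1.96) = 0.806 (0.811 if n replaces the residual degrees of freedom)

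The stated 0.81 is reproduced. It uses ECAS members only, so the make-up of the comparator cannot alter it.

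**2. Eligibility of a person reached only on Instagram or Twitter.** Take an adult Facebook user who lived in Essex during the first lockdown, consents, and saw ECAS only on Instagram.

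| Rule | Result |
|---|---|
| Age, Facebook use, Essex, consent | met |
| Prose: did not sign up to the page | met |
| Prose: does not recall exposure to the page | met |
| List: not enrolled in page and group on Facebook | met |
| Any rule on Instagram or Twitter | none stated |

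This person enters the comparator. No measure in Table 1 would identify the Instagram contact.

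**3. Direction and form of the bias.** Let δ be the true difference, c the share of comparators reached on another channel, and f the fraction of the ECAS effect they receive. The comparator mean moves by c·f·δ, so the expected observed difference is δ(1 − c·f). With f = 1, the worst case for a given c, the difference shrinks by the share c, and a cost per unit of improvement is multiplied by 1/(1 − c): 1.05 at 5%, 1.11 at 10% and 1.25 at 20%.

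**4. Illustration of size.** The protocol gives no between-group effect and no Instagram or Twitter audience, so δ, c and f below are assumptions. With 225 per group, SE = √(2/225) = 0.0943 SD. The difference detectable with 80% power is (1.960 + 0.842) × 0.0943 = 0.264 SD. Power = Φ(δ(1 − c)/0.0943 − 1.96), with f = 1:

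| c | Difference if δ = 0.264 | Power, δ = 0.264 | Power, δ = 0.30 | Power, δ = 0.50 |
|---|---|---|---|---|
| 0% | 0.264 | 0.80 | 0.89 | 1.00 |
| 2% | 0.259 | 0.78 | 0.88 | 1.00 |
| 5% | 0.251 | 0.76 | 0.86 | 1.00 |
| 10% | 0.238 | 0.71 | 0.82 | 1.00 |
| 20% | 0.211 | 0.61 | 0.72 | 0.99 |
| 30% | 0.185 | 0.50 | 0.61 | 0.96 |

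If contact on another channel carried half the effect (f = 0.5), then at c = 5% the difference is 0.264 × 0.975 = 0.257 SD and power is about 0.78.

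**The case against.** The strongest reply is that the exposure under test is Facebook itself. The project aim speaks of the Facebook approach, the intervention is described as a page and a private group, the within-ECAS analysis tests engagement with those two, and Table 1 refers to the site. On that reading, an Instagram or Twitter post is a co-exposure and not a misclassified member. This has real weight and the protocol does not settle it. But the between-group contrast is worded as engagement with the intervention, and the health-equity section counts the other platforms as access to that same intervention. Even on the narrower reading, the co-exposure goes unmeasured.

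The second reply is that the affected group is probably small. To contaminate, a person must be a Facebook user recruited through Facebook, reached by ECAS elsewhere, and neither signed up to nor recalling the Facebook page. Facebook is called the core provision, and the page had 55,339 followers. The other platforms are said only to have presented information, whereas the hypothesised mechanism runs through social connection. These points limit the size and argue against f = 1. They do not close the route.

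The third reply is that excluding everyone who recalls any ECAS content could leave comparators less engaged with online health information. In a non-randomised convenience comparison that could push the contrast away from zero. This stands, and the fix has to allow for it.

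A reader might also infer that one person is classified as an ECAS user in the health-equity analysis and as unexposed in the survey. The documents do not support that. The health-equity work compares demographic profiles and the comparator is a newly recruited sample, with no individuals linked between them. Nor is the questionnaire item available, so nothing can be said about what the survey actually asks. The point concerns the stated definition and criteria.

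**Conclusion.** The gap is real: the stated rules admit people whom ECAS reached only on Instagram or Twitter, and nothing planned would detect them. If ECAS has an effect, the bias is towards no difference, by the fraction c·f. The conclusion rests on taking the contrast as the protocol words it, that is, engagement with the intervention as a whole.

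The size is unknown and may be negligible. A reader might take the power table as evidence that the comparison is underpowered, but the 0.264 SD, the contamination shares and the full-effect assumption have no source in the protocol. With a difference of 0.50 SD, power stays at or above 0.96 even at 30% contamination. It would equally be wrong to infer that the sample-size justification fails, because the 0.81 concerns ECAS members alone. This is an inexpensive improvement to a group definition, not a flaw that invalidates the comparison.

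**What to change.** - In both the prose and the criteria list, define the comparator as people who have not joined, followed or recalled ECAS content on any ECAS channel, naming the Facebook page, the Facebook group, Instagram and Twitter. This also puts the recall condition into the list.
- Ask every comparator respondent about exposure on each channel and record the answer, so that the share c is known.
- Let respondents who report only Instagram or Twitter exposure complete the survey. Leave them out of the main contrast, and report the contrast with and without them.

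The cost is one extra survey item and slightly more people lost from the main contrast, so a few more must be recruited to keep 225 unexposed. The remaining comparators may be less engaged with health information. The paired results would show whether excluding the exposed respondents moves the estimate.

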Essex Coronavirus Action Support (ECAS) involves collaboration between Essex County Council (ECC) and The Essex Public Health Team as well as local Facebook groups. It focuses on the provision of three services: *preventing* the spread of infection, *informing* Essex residents of guidance and *assisting* residents who may be vulnerable. The ECAS Facebook page which was created on 14th March 2020 ('Essex Coronavirus Action', 2020) is now followed by 55,339 people (at the time of writing) and is used to distribute information to the community. The related private group created on 15th March 2020 has approximately 37,900 members ('Essex Coronavirus Action Support', 2020) and is described as a space for residents of Essex, promoting connection and discussion about issues related to the COVID-19 pandemic.

When membership of the ECAS group is requested, admins ask for a postal code to verify people are Essex residents, members are not actively recruited. Whilst approximately 80% of the demographic is female, men have been reported to be over-represented in discussion ('Mobilizing Essex residents', 2020). There are 18 community admins who oversee the private group, three have a prominent role with ECC paying for their work. Issues around misinformation are dealt with on a case-by-case basis and in rare instances members are banned/ muted if promoting argument.

Growth, recruitment and management have been described as evolving intuitively and some research has been conducted to capture decisions explicitly in terms of team roles, structure and the organisational environment ('Essex County Council', 2021). The co-produced logic model illustrating resources, activities and outcomes as well as their connection (shown in Figure 1) guides the current evaluation of the ECAS intervention.

The proposed evaluation will combine quantitative (Work Package 1, see *Methods* below) and qualitative (Work Package 2) methods to understand the extent to which ECAS achieved its aims to facilitate 'prevent, perform and assist' and also the wider impact it has had on public health system approaches.

Rationale

Promoting behavioural change

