COVID protective behaviours	Engage in behaviours which are likely to reduce infection risk to self and others	Self-report (critical phase)	Items from Freeman et al. (2020)
Community champion activity	Helped others practically in real world Signposted to online reliable information Corrected misinformation online	Self-report (critical phase)	Study generated scale
Mental health	Level of anxiety Satisfaction with life COVID specific anxiety syndrome	Self-report (critical phase)	GAD-7 (7 items) PHQ-9 (9 items) SWLS (~5 items) Nikčević & Spada (2020)
	Level of anxiety	Self-report (current state)	GAD-7 (7 items)

¹ Use of tools is subject to securing permissions, where required, from authors.

The relationships highlighted in Figure 2 will be analysed using the Hayes PROCESS macro tool (Hayes, 2018), focusing on one effect and mediation per model (see power analysis below for a rationale).

This aspect of the research will also take additional *secondary outcome measures* from those who engaged with ECAS including *sense of ownership of the site* (self, community, local authority), *understandings of information provenance*, *confidence in information*, *frequency of referrals made to the site* and *reliance upon site*. This will allow exploratory testing of how these factors relate to the efficacy of the intervention. These will need to be short measures (i.e., single item scales) given the length of the primary outcome measures and subsequent possible impact upon participant attrition.

Analysis of existing data

Social network analysis: We will explore the feasibility of using social network analysis (SNA) to see the extent to which influence (categorised as interactions) in the network is central (via admins out to members) or distributed (member to members, including core member and peripheral members) over a given time period (see *Sampling*, below). Data will be analysed using the SNA package on R.

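### Vulnerability to COVID is a plausible but unrecorded confounder of the ECAS–comparator contrast and of the engagement paths among members; its size and direction are unknown, and a short survey item would let it be adjusted for.

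*Protocol*

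**What the plan says.** The protocol's section on the intervention of interest gives ECAS three services: prevention, information, and assistance to "residents who may be vulnerable". Residents ask to join; nobody is recruited into the group.

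Under Sampling, the plan for Work Package 1 reads: "We will aim to recruit a sample of $n = 225$ people who have signed up to the ECAS Facebook page and group". The other arm is described this way, the ECAS page being what is meant at the end: "We will also recruit a comparative, equally sized sample of Facebook users who did not sign up to the page nor recall being exposed to". On comparability of the two samples it says: "These will be either a comparative demographic profile, or we will weight responses to match our samples". The section on sampling technique adds only that weighting will be explored if the sample proves unrepresentative.

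Table 1 lists engagement, social connection, digital health literacy, protective behaviour, community champion activity and mental health. Protective behaviour is defined as "Engage in behaviours which are likely to reduce infection risk to self and others". Community champion activity has three parts, the first being "Helped others practically in real world"; the other two, signposting and correcting misinformation, take place online. Neither Table 1, the secondary measures nor the eligibility criteria mention vulnerability, health risk or advice to stay at home.

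The theoretical framework accepts that confounding has to be handled, but the confounders it names are wellbeing and lifestyle. The mediation models are to be fitted "focusing on one effect and mediation per model".

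**The concern.** Residents at high risk, or living with someone at high risk, may have their own reason to join ECAS and to use it more. The same status may change outcomes directly, for example by making people more cautious whatever they read. Two residents of the same age and sex can differ in risk, so a demographic match does not guarantee balance on it.

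Both the ECAS–comparator contrast and the engagement paths among members would then mix the effect of ECAS with the effect of need. These analyses are meant to show how far ECAS met its aims and which outcomes moved most. A confounder that acts differently on different outcomes would distort that ranking. The same outcomes and comparator also feed the cost per unit of change in Work Package 3. A larger sample would not remove the bias.

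**Working it through.** **The plan's own figure.** The section on size of sample says that 225 members "allows detection of single mediation effects at power = 0.81 assuming medium (Pearson $r = .30$) relationships between variables". With two-sided alpha 0.05 (assumed; not stated) and all three correlations .30, the Sobel formula gives:

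- a = .30; b = (.30 − .09)/(1 − .09) = 0.231; ab = 0.0692.
- With n = 225 as divisor, z = 2.840 and power = 0.811. With residual degrees of freedom, z = 2.824 and power = 0.806.

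The stated 0.81 reproduces. It concerns mediation within the ECAS sample and says nothing about confounding.

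**The group contrast.** Inputs from the protocol are 225 v 225.

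- SE of a standardised difference = sqrt(2/225) = 0.0943, before any loss from weighting.
- Difference detectable with 80% power = (1.960 + 0.842) × 0.0943 = 0.264 SD.

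**Bias from an unmeasured binary confounder.** Bias in SD = (share vulnerable in ECAS − share vulnerable in comparator) × effect of vulnerability on the outcome in SD. With no true ECAS effect, the false rejection rate is P(|Z + bias/SE| > 1.96). The documents supply neither the shares nor the effect, so every value in the first two columns is assumed.

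| Share, ECAS v comparator | Effect (SD) | Bias (SD) | False rejection |
|---|---|---|---|
| 20% v 15% | 0.2 | 0.01 | 5.1% |
| 25% v 15% | 0.5 | 0.05 | 8.3% |
| 35% v 15% | 0.5 | 0.10 | 18.5% |
| 30% v 15% | 0.8 | 0.12 | 24.7% |
| 40% v 15% | 0.8 | 0.20 | 56.4% |
| 15% v 15% | any | 0 | 5.0% |
| 15% v 25% | 0.5 | −0.05 | 8.3% |

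The middle case, 10–20 points with 0.5 SD, is 0.05/0.264 = 19% to 0.10/0.264 = 38% of the detectable difference.

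**Community champion scale.** Suppose its three parts are standardised and summed with equal weight, and vulnerability shifts only practical help, by 0.5 SD. The SD of the sum is sqrt(3 + 6r), where r is the correlation between parts.

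- 10 points, r = .5: 0.05/2.449 = 0.02 SD, false rejection about 5.5%.
- 20 points, r = 0: 0.10/1.732 = 0.06 SD, false rejection about 9%.

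**Engagement path among members.** If vulnerability correlates .20 with engagement and .20–.30 with the outcome (assumed), the spurious correlation is .20 × .20 = .04 to .20 × .30 = .06. By Fisher's z at n = 225, with SE = 1/sqrt(222), false rejection is 9.2% to 14.6%.

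**The case against.** A reader might infer that joining does track need, and that the contrast is therefore pushed up for protective behaviour and down for practical help, making the pattern across outcomes an artefact. The documents do not support that. Nothing shows that vulnerable residents are over-represented among members or engage more. The group is described as a place for Essex residents in general to connect and discuss, so people inclined to give help may be drawn to it too, which would push practical help up. Practical help is also only one of three champion components. This part of the objection stands in full.

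A reader might also take the one-mediation-per-model rule to bar covariates. It does not: it limits mediators, and the sample size section explains that multiple mediation is out of reach. Covariate lists are commonly left to an analysis plan. That is also right, but an analysis plan cannot adjust for something that was never asked.

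Table 1 is headed as indicative and omits age and sex as well, which the study must collect. So absence from the table is not proof that the survey will lack the item. This stands in part. Demographics are called for elsewhere in the protocol, whereas vulnerability is mentioned only as a purpose of ECAS.

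Weighting that includes age may absorb some of the imbalance. The listed anxiety measures are not a substitute: they are not named for adjustment, and they refer to times after ECAS was set up, so ECAS may have influenced them.

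Finally, the middle-case bias is modest beside a detectable 0.264 SD, and .04–.06 is small beside the .30 powered for. That argues for a light remedy, not for none.

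**Conclusion.** The point holds as a gap in what the plan records. Membership is self-selected, one service is aimed at people with a particular need, the only stated control is demographic, and no listed measure captures that need. As written, the plan leaves confounding by vulnerability uncontrolled in both the group contrast and the within-member paths.

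Size and sign are not established. Under the assumed 10–20 point imbalance and 0.5 SD effect, a standardised contrast is biased by 0.05–0.10 SD, with 8–19% false rejection. Over the wider assumed range the bias runs from 0.01 to 0.20 SD. It is zero if the shares are equal and reversed if the comparator sample is the more vulnerable. For the champion scale it is smaller (about 0.02–0.06 SD) and its direction is open. This is a worthwhile, inexpensive improvement; it does not show that the comparison will mislead.

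**What to change.** Add a short item to the survey for both samples. It should ask, separately for the respondent and for household members, whether they were at high risk from COVID or advised to stay at home for that reason. The reference time should be the start of the first lockdown or before joining ECAS. The later critical phase is unsuitable, because ECAS was by then informing residents and could have changed perceived risk; adjusting for that would remove part of any effect. The two answers should be kept apart, since being at risk and living with someone at risk may act differently on helping others.

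Add the item to the variables used for matching or weighting. Enter it, with age and sex, as a covariate in the mediator and outcome equations of the PROCESS models and in the ECAS–comparator comparison. Present the direction of any remaining bias as a hypothesis, with a range like the one above.

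The cost is one more recalled answer, with its recall error, and a negligible loss of degrees of freedom: four covariates take the outcome equation among members from 225 − 3 = 222 to 218. The target of 450 need not change.
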